	
General Exclusion Criteria for All Parts:
 
 1. Lactating or pregnant female. 2. History of another malignancy including resected non-melanomatous skin cancer. 3. Subjects with Neurofibromatosis Type-1 (NF-1) associated optic pathway tumors are excluded if they are actively receiving therapy for the optic pathway tumor or do not meet criteria for Plexiform Neurofibroma or malignant solid tumor. 4. Subjects with a history of NF-1 related cerebral vascular anomaly (such as Moyamoya). 5. Subjects with NF-1 actively receiving therapy for the optic pathway tumor 6. Subjects with NF-1 and only Plexiform Neurofibroma (PN) lesions that cannot be evaluated by volumetric analysis. 7. Any serious and/or unstable pre-existing medical, psychiatric disorder or other conditions that could interfere with subject's safety, obtaining informed consent or compliance to the study procedures. 8. Any prohibited medication(s) as described in Section 9.2. 9. Any medications for treatment of left ventricular systolic dysfunction 10. Part B cohorts 1, 2 and 3: Previous treatment with dabrafenib, trametinib or another MEK inhibitor (exception: prior treatment with sorafenib is permitted). Patients who have had prior dabrafenib therapy may enroll into cohort B4. Patients who have had prior dabrafenib therapy and had benefit from that therapy as determined by the investigator, are allowed in Part C or Part D 11. Administration of an investigational study treatment within 30 days preceding the first dose of study treatment(s) in this study. 12. Have a known hypersensitivity reaction or idiosyncrasy to drugs chemically related to study treatment or excipients that contraindicate their participation. 13. Current active liver or biliary disease (with the exception of Gilbert's syndrome or asymptomatic gallstones, or liver metastases). 14. History of hepatic sinusoid obstructive syndrome (Venoocclusive disease) within the prior 3 months. 15. History of heparin-induced thrombocytopenia. 16. History of interstitial lung disease or pneumonitis. 17. History of or current evidence of retinal vein occlusion (RVO) 18. For subjects with solid tumors that are not primary central nervous system (CNS) tumors or NF-1 associated plexiform neurofibromas, subjects with symptomatic or untreated leptomeningeal or brain metastases or spinal cord compression are excluded. 19. A history of known Human Immunodeficiency Virus (HIV), Hepatitis B Virus (HBV), or Hepatitis C Virus (HCV) infection. 20. Unresolved toxicity of National Cancer Institute Common Terminology Criteria for Adverse Events, version 4.0 (NCI CTCAE v4.0) [NCI, 2009] Grade 2 or higher from previous anti-cancer therapy, except alopecia. 21. Presence of active gastrointestinal disease or other condition that will interfere significantly with the absorption of drugs. If clarification is needed as to whether a condition will significantly affect absorption of drugs, contact the Medical Lead for guidance to enrol the subject. 22. A history or evidence of cardiovascular risk (as detailed in protocol Section 5.2.2)

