5.2.1.3 Specific Eligibility Criteria, Part B

Subjects must meet General Eligibility Criteria. The specific eligibility criteria listed here will apply to subjects enrolling to different cohorts of Part B.

1. Tumor tissue (archived or fresh) is required and must be available to be shipped to Novartis or site specific laboratory except in subjects where tumor biopsy is not possible.
2. **Solid Tumor Cohort (B1) Specific Criteria:**

- Histologically confirmed neuroblastoma which have been associated with MAPK/RAS/MEK activation. Histological confirmation may be at diagnosis or recurrence. Laboratory documentation of pathway activation is not required; however, archival tissue is requested at the time of enrollment.
- Measurable or evaluable tumors. Subjects with neuroblastoma that is only detectable by MIBG scan are eligible if they have at least one lesion that can be assessed using the Curie scale. Subjects with neuroblastoma that is only detected by bone marrow aspirate/biopsy or elevated HVA/VMA are not eligible.
- If neuroblastoma subjects have only one MIBG positive lesion and that lesion was radiated (external beam or systemic radiolabeled ¹³¹I-MIBG), a biopsy must be done at least 28 days after radiation was completed and must show viable neuroblastoma
- *Hematological Toxicity Evaluable Subjects* (at least 6 of cohort of 10) must have adequate bone marrow function defined as:
 - Absolute neutrophil count (ANC) $\geq 1000/\mu\text{L}$;
 - Hemoglobin ≥ 8.0 g/dL (may receive red blood cell transfusions)
 - Platelets $\geq 75,000/\mu\text{L}$ (transfusion independent, defined as not receiving platelet transfusions within a 7 day period prior to enrollment)
- *Hematological Toxicity Inevaluable Subjects* (up to 4 in a cohort of 10) must have adequate bone marrow function defined as:
 - Absolute neutrophil count (ANC) $> 500/\mu\text{L}$;
 - Hemoglobin ≥ 8.0 g/dL (may receive red blood cell transfusions)
 - Platelets $> 25,000/\mu\text{L}$ (transfusion independent, defined as not receiving platelet transfusions within a 7 day period prior to enrollment)

3. BRAF Fusion Cohort (B2) Specific Criteria:

- Relapsed or refractory gliomas or other primary brain tumors with BRAF fusion/duplication (documented in Clinical Laboratory Improvement Amendments (CLIA) certified or equivalent laboratory) or NF1 subjects with gliomas who are not suitable for the NF1 with PN cohort.
- Adequate hematologic function defined as:

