- Subjects must have measurable PN(s) amenable to volumetric MRI analysis. For the purpose of this study, the target lesion must be seen on at least 3 consecutive MRI slices and the field of view must contain the entire tumor of interest. Tumors must be at least 3 mL in volume (most PNs 3 cm in longest diameter will meet this criteria). If the tumor is <3 cm in longest diameter, the subject may still be eligible. Central review of the MRI of the target PN is required prior to enrollment to ensure that the tumor is measurable and amenable to volumetric analysis. After consenting, please follow instructions in [Appendix 6](#) or the SPM for central review of MRI. Central review will take 3-7 days (please plan accordingly).
- Adequate hematologic function defined as:
 - Absolute neutrophil count (ANC) $\geq 1000/\mu\text{L}$;
 - Hemoglobin ≥ 8.0 g/dL (may receive red blood cell transfusions)
 - Platelets $\geq 75,000/\mu\text{L}$ (transfusion independent, defined as not receiving platelet transfusions within a 7 day period prior to enrollment)
- Subjects with NF-1 and PN will only be eligible if complete tumor resection is not feasible, or if a subject with a surgical option refuses surgery.
 - Since there is no standard effective chemotherapy for subjects with NF-1 and PN, subjects may be treated on this trial without having received prior medical therapy directed at their PN.
 - Must not have received myelosuppressive chemotherapy within prior 4 weeks.
 - Must be at least 2 weeks since undergoing major surgery and must be recovered from effects of surgery.

- Subjects who have received previous investigational agents or biologic therapy, such as tipifarnib, pirfenidone, Peg-Intron, sofenib, imatinib or vascular endothelial growth factor receptor (VEGFR) or MEK inhibitors are eligible for enrolment if general eligibility criteria are met.
- Subjects who have received therapy for PN that included other MAPK/MEK /RAS inhibitors are eligible for this study.

5. BRAF V600 mutant solid tumors Cohort (B4) Specific Criteria:

- Male or female ≥ 12 months and < 18 years of age at the time of signing the informed consent form;
- BRAF V600 mutation-positive tumor as confirmed in a CLIA-approved laboratory or equivalent. Subjects may be enrolled based on local test results. Note: all subjects must provide archival or fresh tumor tissue at screening for central confirmation of local test derived BRAF V600 mutation status.

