5.2.2 Exclusion Criteria (All Parts)

Deviations from exclusion criteria are not allowed because they can potentially jeopardize the scientific integrity of the study, regulatory acceptability or subject safety. Therefore, adherence to the criteria as specified in the protocol is essential.

Subjects meeting any of the following criteria must not be enrolled in the study:

1. Lactating or pregnant female.
2. History of another malignancy including resected non-melanomatous skin cancer.
3. Subjects with NF-1 associated optic pathway tumors are excluded if they are actively receiving therapy for the optic pathway tumor or do not meet criteria for PN or malignant solid tumor
4. Subjects with a history of NF-1 related cerebral vascular anomaly (such as Moyamoya)
5. Subjects with NF-1 actively receiving therapy for the optic pathway tumor.
6. Subjects with NF-1 and only PN lesions that cannot be evaluated by volumetric analysis (only applicable to Part B).
7. Any serious and/or unstable pre-existing medical, psychiatric disorder or other conditions that could interfere with subject's safety, obtaining informed consent or compliance to the study procedures.
8. Any prohibited medication(s), currently used or expected to be required, as described in [Section 9.2](#).
9. Any medications for treatment of left ventricular systolic dysfunction

10. Part B, C and D: Previous treatment with dabrafenib or any BRAF inhibitor, trametinib or another MEK inhibitor, or an ERK inhibitor (exception: prior treatment with sorafenib is permitted). Patients who have received prior dabrafenib or another BRAF inhibitor may enrol into Part B4. Patients who have had prior dabrafenib or BRAF inhibitor therapy may enroll in part C or Part D if they have had prior benefit to dabrafenib or BRAF inhibitor monotherapy, as determined by the investigator. (Note: Subjects enrolled in Parts A or B are not eligible to participate in Parts C or D)
11. Administration of an investigational study treatment within 30 days preceding the first dose of study treatment(s) in this study.
12. Have a known immediate or delayed hypersensitivity reaction or idiosyncrasy to drugs chemically related to study treatment or excipients that contraindicate their participation.
13. Current active liver or biliary disease (with the exception of Gilbert's syndrome or asymptomatic gallstones, or liver metastases).
14. History of hepatic sinusoid obstructive syndrome (venoocclusive disease) within the prior 3 months.

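### The B3 criteria admit subjects with prior MEK-inhibitor treatment while exclusion 10 and the synopsis bar them, so the population behind the B3 response rate is not uniquely defined on prior MEK-inhibitor exposure

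*Protocol*

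**What the plan says.** **Text that admits.** Two bullets in the B3 part of section 5.2.1.3 deal with earlier targeted therapy. The first lists previous investigational or biologic agents and ends with "or MEK inhibitors are eligible for enrolment if general eligibility criteria are met". The second carries no condition: "Subjects who have received therapy for PN that included other MAPK/MEK /RAS inhibitors are eligible for this study".

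**Text that bars.** Section 5.2.2, which applies to all parts, opens with "Subjects meeting any of the following criteria must not be enrolled in the study". Its item 10 reads "Part B, C and D: Previous treatment with dabrafenib or any BRAF inhibitor, trametinib or another MEK inhibitor, or an ERK inhibitor". Prior sorafenib is excepted. Within Part B the only other exception is "Patients who have received prior dabrafenib or another BRAF inhibitor may enrol into Part B4", and the Part C and Part D exceptions likewise concern prior dabrafenib or another BRAF inhibitor. B3 has no exception. Item 10 of the synopsis exclusion list is narrower in scope but names the cohort: "Part B cohorts 1, 2 and 3: Previous treatment with dabrafenib, trametinib or another MEK inhibitor".

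**Force of the criteria.** Sections 5.2.1 and 5.2.2 do not allow deviations from inclusion or exclusion criteria, and section 3.1 does not allow waivers.

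**Use of the data.** Section 3.9.4 counts preliminary activity among the primary endpoints of Part B, although Table 2-1 lists tumor response as secondary. Section 12.2.2 plans at least 10 evaluable subjects per cohort and treats fewer than one response as possibly insufficient activity. Section 12.4.2 gives B3 its own interim analysis, which informs future development and may be published. Under section 3.10.1, responses of Part A subjects treated at the recommended phase 2 dose (RP2D) are considered with the matching Part B cohort.

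**The concern.** A subject whose PN was previously treated with a MEK inhibitor other than trametinib is eligible under one section and barred under another. Trametinib is itself a MEK inhibitor, so earlier exposure to the class bears directly on how its response rate is read. A rate in subjects never exposed to the class and a rate in a mixed group answer different questions.

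In a cohort of about 10, each subject carries up to 10 percentage points of the observed rate, and B3 results feed development decisions and possibly publications. A reader of those results could not tell from the protocol which of the two populations the rate describes.

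**Working it through.** **1. The passages side by side**

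| Place | Prior MEK inhibitor, cohort B3 |
|---|---|
| 5.2.1.3, B3, first bullet | Eligible, if the general eligibility criteria are met |
| 5.2.1.3, B3, second bullet | Eligible, no condition |
| 5.2.2, item 10 | Barred (Parts B, C and D) |
| Synopsis, item 10 | Barred (cohorts 1, 2 and 3 named) |

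**2. Can they be read together?** The condition in the first bullet does not resolve the conflict. General Eligibility Criteria is the title of section 5.2.1.1, an inclusion list, and not of the exclusion list in 5.2.2. The second bullet lacks even that condition. Nor can the exclusion be taken as a broad statement about Part B that overlooked B3, because the synopsis names cohort 3. No precedence rule is given.

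**3. The Part A route.** Section 5.2.1.2 admits NF-1 associated PN to Part A, and exclusion 10 does not cover Part A in either the body or the synopsis. Under section 3.10.1, a MEK-pretreated PN subject treated in Part A at the RP2D could therefore be considered with B3 whichever B3 text was followed. Rewording the B3 criteria alone would not settle the composition of that analysis.

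**4. The plan's own figures.** Table 12-2 gives P(0 of 10 responses) = (1 − p)^10. At p = 0.20 this is 0.8^10 = 0.107, so P(at least 1) = 0.893; the table has 0.11 and 0.89. All 12 entries of Table 12-2 and all seven intervals of Table 12-3 reproduce. These figures are correct and are not in dispute.

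**5. Size under stated assumptions.** The documents give neither the number of pretreated B3 subjects nor an expected response rate for them. Let k of 10 be pretreated, with response rate q, and the rest MEK-inhibitor-naive, with rate p = 20% (assumed).

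- Expected cohort rate = [(10 − k)p + kq] / 10
- P(at least 1 response) = 1 − (1 − p)^(10 − k) × (1 − q)^k

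For k = 3 and q = 0: 7 × 0.20 / 10 = 14%, and 1 − 0.8^7 = 0.79. For k = 3 and q = 10%: (7 × 0.20 + 3 × 0.10) / 10 = 17%, and 1 − 0.8^7 × 0.9^3 = 0.85.

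| Pretreated of 10 | Expected rate, q = 0% | P(≥1), q = 0% | Expected rate, q = 10% | P(≥1), q = 10% |
|---|---|---|---|---|
| 0 | 20% | 0.89 | 20% | 0.89 |
| 2 | 16% | 0.83 | 18% | 0.86 |
| 3 | 14% | 0.79 | 17% | 0.85 |
| 5 | 10% | 0.67 | 15% | 0.81 |

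The first row is the case in which the contradiction had no effect on enrolment.

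**The case against.** **The exclusion list governs.** Eligibility is normally conjunctive, and 5.2.2 says that meeting any one exclusion bars enrolment. A site applying both lists would not enrol the subject. That is a plausible working reading, but it leaves the MEK-inhibitor wording in both B3 bullets without effect, and no text says it is the intended one.

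**The analysis set is defined.** This stands. Sections 12.3.1 and 12.5.1 use the All Treated Population for activity, with the Response-evaluable Population as sensitivity analysis. A reader might infer that the B3 response rate has no defined population at all. The documents do not support that: the denominator is fixed, and only the eligible population is unclear, on this one characteristic.

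**No harm is shown.** This also stands. A reader might infer that some sites enrolled subjects wrongly, or that the B3 rate cannot be interpreted. Both presuppose that pretreated subjects entered B3, which the protocol does not say.

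**Little can change now.** Part B is descriptive with no hypothesis test (12.1.2), the B3 interim does not affect study conduct (12.4.2), and all cohorts are closed (Amendment 9 rationale). Subgroup reporting is commonly left to the SAP, which is not shown, so its absence from the protocol is no fault. These points lower the priority. They do not remove the contradiction, and closed enrolment means that reporting has to carry the remedy.

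**A similar conflict in B2?** A reader might see one between the B2 criterion admitting "NF1 subjects with gliomas who are not suitable for the NF1 with PN cohort" and exclusion 3, which removes NF-1 optic pathway tumors that are under active therapy or "do not meet criteria for PN or malignant solid tumor". That does not follow. Exclusion 3 concerns only optic pathway tumors, NF-1 gliomas elsewhere remain eligible, and both texts can be obeyed together. It is an ordinary inclusion narrowed by an exclusion.

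**Conclusion.** The contradiction is real in the current text: two B3 bullets admit what exclusion 10 and the synopsis bar. The population to which the B3 response rate applies is therefore not uniquely defined with respect to prior MEK-inhibitor exposure.

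The consequence may be nil. If pretreated subjects are present, the illustrations with an assumed naive rate of 20% lower the expected rate by 2 to 10 points for 2 to 5 pretreated subjects in 10, and by 3 to 6 points for 3. Those shifts are small beside the exact interval at this size (2.5% to 55.6% for 2 of 10 in Table 12-3), so the matter is mainly one of what the rate means. It is more than clerical, because B3 has its own interim analysis for development decisions. It should be settled before B3 results are reported, but it does not undermine the study.

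**What to change.** 1. Reconcile the two B3 bullets in 5.2.1.3 with exclusion 10 in 5.2.2 and item 10 of the synopsis, so that one rule on prior MEK-inhibitor treatment applies to B3. Which rule is right is for the sponsor to decide.
2. State how many B3 subjects had prior MEK-inhibitor exposure, and how many Part A PN subjects at the RP2D considered with B3 under 3.10.1 did. Section 9 already requires a complete list of prior anti-cancer therapies in the eCRF, so no new data collection is planned here.
3. Report response with exact confidence intervals overall and in MEK-inhibitor-naive subjects. If the count in step 2 is zero, a sentence saying so is enough.

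The cost is a text clarification and one extra table. Intervals in small subgroups will be wide: for 0 of 3 responders the exact 95% upper limit is 1 − 0.025^(1/3) = 71%. The split describes who was studied and would not support a comparison between the two groups.

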5.2.1.4 Specific Eligibility Criteria, Part C

Subjects must meet General Eligibility Criteria.

1. Tumors that have been documented by CLIA or equivalent certified laboratory test to harbor BRAF V600 mutation at diagnosis or relapse.
2. Subjects may be enrolled based on local test results. Note: all subjects must provide archival or fresh tumor tissue at screening for central confirmation of local test derived BRAF V600 mutation status.
3. Measurable or evaluable disease.
4. Adequate bone marrow function defined as:
 - Absolute neutrophil count (ANC) $\geq 1000/\mu\text{L}$;
 - Hemoglobin ≥ 8.0 g/dL (may receive red blood cell transfusions);
 - Platelets $\geq 75,000/\mu\text{L}$ (transfusion independent, defined as not receiving platelet transfusions within a 7 day period prior to enrollment).

- PT/INR and PTT $\leq 1.3 \times$ ULN; subjects receiving anticoagulation treatment may be allowed to participate with INR established within the therapeutic range prior to starting study medication

5.2.1.5 Specific Eligibility Criteria, Part D

Subjects must meet General Eligibility Criteria.

1. Measurable or evaluable disease.
2. Recurrent or refractory BRAF mutant LGG or LCH tumors
3. BRAF V600 mutation confirmed in a CLIA-approved laboratory or equivalent. Subjects may be enrolled based on local test results. Note: all subjects must provide archival or fresh tumor tissue at screening for central confirmation of local test derived BRAF V600 mutation status.
4. Adequate bone marrow function defined as:
 - Absolute neutrophil count (ANC) $\geq 1000/\mu\text{L}$;
 - Hemoglobin ≥ 8.0 g/dL (may receive red blood cell transfusions);
 - Platelets $\geq 75,000/\mu\text{L}$ (transfusion independent, defined as not receiving platelet transfusions within a 7 day period prior to enrollment).
 - PT/INR and PTT $\leq 1.3 \times$ ULN; subjects receiving anticoagulation treatment may be allowed to participate with INR established within the therapeutic range prior to starting study medication

5.2.2 Exclusion Criteria (All Parts)

Deviations from exclusion criteria are not allowed because they can potentially jeopardize the scientific integrity of the study, regulatory acceptability or subject safety. Therefore, adherence to the criteria as specified in the protocol is essential.

Subjects meeting any of the following criteria must not be enrolled in the study:

1. Lactating or pregnant female.
2. History of another malignancy including resected non-melanomatous skin cancer.
3. Subjects with NF-1 associated optic pathway tumors are excluded if they are actively receiving therapy for the optic pathway tumor or do not meet criteria for PN or malignant solid tumor
4. Subjects with a history of NF-1 related cerebral vascular anomaly (such as Moyamoya)
5. Subjects with NF-1 actively receiving therapy for the optic pathway tumor.
6. Subjects with NF-1 and only PN lesions that cannot be evaluated by volumetric analysis (only applicable to Part B).
7. Any serious and/or unstable pre-existing medical, psychiatric disorder or other conditions that could interfere with subject's safety, obtaining informed consent or compliance to the study procedures.
8. Any prohibited medication(s), currently used or expected to be required, as described in [Section 9.2](#).
9. Any medications for treatment of left ventricular systolic dysfunction

10. Part B, C and D: Previous treatment with dabrafenib or any BRAF inhibitor, trametinib or another MEK inhibitor, or an ERK inhibitor (exception: prior treatment with sorafenib is permitted). Patients who have received prior dabrafenib or another BRAF inhibitor may enrol into Part B4. Patients who have had prior dabrafenib or BRAF inhibitor therapy may enroll in part C or Part D if they have had prior benefit to dabrafenib or BRAF inhibitor monotherapy, as determined by the investigator. (Note: Subjects enrolled in Parts A or B are not eligible to participate in Parts C or D)
11. Administration of an investigational study treatment within 30 days preceding the first dose of study treatment(s) in this study.
12. Have a known immediate or delayed hypersensitivity reaction or idiosyncrasy to drugs chemically related to study treatment or excipients that contraindicate their participation.
13. Current active liver or biliary disease (with the exception of Gilbert's syndrome or asymptomatic gallstones, or liver metastases).
14. History of hepatic sinusoid obstructive syndrome (venoocclusive disease) within the prior 3 months.
15. History of heparin-induced thrombocytopenia.
16. History of interstitial lung disease or pneumonitis.
17. History or current evidence RVO
18. For subjects with solid tumors that are not primary CNS tumors or NF-1 associated plexiform neurofibromas, subjects with symptomatic or untreated leptomeningeal or brain metastases or spinal cord compression are excluded.

NOTE: Subjects previously treated for these conditions that have had stable CNS disease (verified with consecutive imaging studies) for >3 months, are asymptomatic and are not currently taking corticosteroids, or are on stable dose or decreasing of corticosteroids for at least 7 days prior to enrolment are permitted.

19. A history of known Hepatitis B Virus (HBV), or Hepatitis C Virus (HCV) infection. Subjects with laboratory evidence of cleared HBV and HCV infection may be enrolled.
20. Unresolved toxicity of National Cancer Institute Common Terminology Criteria for Adverse Events, version 4.03 (NCI CTCAE v4.03) (NCI 2009) Grade 2 or higher from previous anti-cancer therapy, except alopecia.
21. Presence of active gastrointestinal disease or other condition that will interfere significantly with the absorption of drugs. If clarification is needed as to whether a condition will significantly affect absorption of drugs, contact the Novartis Medical Lead for guidance to enrol the subject.
22. A history or evidence of cardiovascular risk including any of the following:
 - A QT interval corrected for heart rate using the Bazett's formula (QTcB) ≥ 480 msec;
 - A history or evidence of current clinically significant uncontrolled arrhythmias;
Clarification: Subjects with atrial fibrillation controlled for >30 days prior to dosing are eligible.
 - A history of acute coronary syndromes (including myocardial infarction or unstable angina), coronary angioplasty, or stenting within 6 months prior to randomization.

- A history or evidence of current \geq Class II congestive heart failure as defined by the New York Heart Association (NYHA) guidelines;
- Patients with intra-cardiac defibrillators;
- Abnormal cardiac valve morphology (\geq grade 2) documented by echocardiogram (subjects with grade 1 abnormalities [i.e., mild regurgitation/stenosis] can be entered on study). Subjects with moderate valvular thickening should not be entered on study. Subjects with prosthetic valves can be considered eligible provided they meet the criteria as stated above.
- Treatment refractory hypertension defined as a blood pressure of systolic $>$ 140 mmHg and/or diastolic $>$ 90 mm Hg (or above 95th age-specific percentile as listed in [Appendix 8](#)), which cannot be controlled by anti-hypertensive therapy;

6 Completion or Withdrawal of Subjects

